## 10.5 ADVERSE EVENTS / SERIOUS ADVERSE EVENT CAUSALITY ASSESSMENT

---

The Investigator must also assess the relationship of any adverse event to the use of study drugs (whether none, one, or both), based on available information, using the following guidelines:

- **Not Related:** Clear-cut temporal and/or mechanistic relation to a cause other than the study drug(s).
- **Doubtful:** There is no reasonable possibility that the event is related to the study drug(s) but a definite cause cannot be ascertained.
- **Possible:** There is still a reasonable possibility that the cause of the event was the study drug(s) but there exists a more likely cause of the event such as complications of progressive disease.
- **Probable:** The most likely cause of the event is the study drug(s) but other causes cannot be completely excluded.
- **Definite:** Clear cut temporal and/or mechanistic relation to the study drug(s). All other causes have been eliminated. Events classified as definite will often be confirmed by documenting resolution on discontinuation of the study drug and recurrence upon resumption.

---

### 10.5.1 RECORDING OF ADVERSE EVENTS

---

All adverse events of any subject during the course of the study will be reported on the case report form, and the investigator will give his or her opinion as to the relationship of the adverse event to

study drug treatment (i.e., whether the event is related or unrelated to study drug administration – ublituximab + umbralisib). If the adverse event is serious, it should be reported as soon as possible and no greater than 24 hours to the sponsor or designee. Other untoward events occurring in the framework of a clinical study are also to be recorded as AEs (i.e., AEs that occur prior to assignment of study treatment that are related to a protocol-mandated intervention, including invasive procedures such as biopsies, medication washout, or no treatment run-in).

All AEs regardless of seriousness or relationship to ublituximab + umbralisib treatment spanning from Cycle 1/Day 1 until 30 calendar days after discontinuation or completion of either protocol-specific treatment as defined by the protocol for that subject, are to be recorded on the eCRF.

---

### 10.5.2 ABNORMAL LABORATORY VALUES AND VITAL SIGNS

---

The reporting of abnormalities of vital signs as adverse events should be avoided. Abnormalities of vital signs should not be reported unless any criterion for an SAE is fulfilled, the vital signs abnormalities cause the subject to discontinue study treatment, or the investigator insists that the abnormality should be reported as an AE. Abnormal laboratory results should be noted in the eCRF as an adverse event if they are associated with an overdose, require or prolong inpatient hospitalization, or are otherwise considered clinically significant by the investigator. If an abnormal laboratory value or vital sign is associated with clinical signs and/or symptoms, the sign or symptom should be reported as an AE, and the associated laboratory value or vital sign should be considered additional information that must be collected in the relevant eCRF. If the laboratory abnormality is a sign of a disease or syndrome, only the diagnosis needs to be recorded on the SAE Report Form or AE eCRF.

Clinical Laboratory Results will be summarized. Summary statistics for actual values and for changes from baseline will be tabulated for laboratory results by scheduled visit. Subjects with laboratory values outside of the normal reference range at any post-baseline assessment will be summarized and graded per NCI CTCAE Version 4.0 when applicable. Subject incidence of abnormal laboratory results will be summarized by treatment group and maximum grade for each abnormal laboratory finding.

---

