### 3.1 INCLUSION CRITERIA

---

1. Prior treatment in clinical trial [UTX-TGR-304](#)
  - a. Confirmed progression by IRC on Arms B, C, or D after at least two cycles of treatment in trial UTX-TGR-304. There is no required timeframe to begin treatment on the UTX-TGR-204 protocol; however, if other therapies to treat the disease are implemented in the interim, the subject will not be eligible to enroll in the study.
  - b. Non-progressing subjects on Arm A may be eligible for enrollment when protocol UTX-TGR-304 is completed.
2. Adequate organ system function, defined as follows:
  - a. Absolute neutrophil count (ANC)  $> 750 \times 10^3/\text{mm}^3$  (0.75 K/ $\mu\text{L}$ ) / platelet count  $> 40 \times 10^3/\text{mm}^3$  (40 K/ $\mu\text{L}$ ) unless cytopenias are related to bone marrow involvement.
  - b. Total bilirubin  $\leq 1.5$  times the upper limit of normal (ULN) with the exception of Gilbert's Disease and Autoimmune Hemolytic Anemia.
  - c. Alanine aminotransferase (ALT) and aspartate aminotransferase (AST)  $\leq 2.5 \times$  ULN if no liver involvement or  $\leq 5 \times$  the ULN if known liver involvement
  - d. Calculated creatinine clearance  $> 30$  mL/min (as calculated by the modified Cockcroft-Gault formula).
3. ECOG performance status  $\leq 2$
4. Ability to swallow and retain oral medication
5. Willingness and ability to comply with trial and follow-up procedures, give written informed consent

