## 8.4 COMPLETE RESPONSE

---

To satisfy criteria for a CR, all of the following criteria must be met:

- No evidence of new disease
- ALC in peripheral blood of  $<4 \times 10^9/L$
- Regression of all target nodal masses to normal size  $\leq 1.5$  cm in the LD
- Normal spleen and liver size
- Regression to normal of all nodal non-target disease and disappearance of all detectable non-nodal, non-target disease

- Morphologically negative bone marrow defined as <30% of nucleated cells being lymphoid cells and no lymphoid nodules in a bone marrow sample that is normocellular for age
- Peripheral blood counts meeting all of the following criteria:
  - ANC  $>1.5 \times 10^9/L$  without need for exogenous growth factors (e.g., G-CSF)
  - Platelet count  $\geq 100 \times 10^9/L$  without need for exogenous growth factors
  - Hemoglobin  $\geq 110 \text{ g/L}$  (11.0 g/dL) without red blood cell transfusions or need for exogenous growth factors (e.g., erythropoietin)

Subjects who fulfill all the criteria for a CR (including bone marrow criteria) but who have a persistent anemia, thrombocytopenia, or neutropenia or a hypocellular bone marrow that is related to prior or ongoing drug toxicity (and not to CLL) will be considered as a CR with incomplete marrow recovery (CRi).

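### The graded laboratory table counts abnormalities present at entry together with new or worsened ones

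*Combined protocol and SAP*

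**What the plan says.** Section 10.5.2 has three sentences on laboratory tabulation.

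- Group summaries: "Summary statistics for actual values and for changes from baseline will be tabulated for laboratory results by scheduled visit".
- The rule for being counted: "Subjects with laboratory values outside of the normal reference range at any post-baseline assessment will be summarized and graded", using CTCAE 4.0 where it applies.
- The incidence table: "Subject incidence of abnormal laboratory results will be summarized by treatment group and maximum grade for each abnormal laboratory finding".

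Only the first refers to the baseline value. The documents plan no shift table and define no treatment-emergent laboratory abnormality.

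Section 3.1 sets the entry limits. Item 2a gives floors for neutrophils (0.75 K/µL in the bracketed figure) and platelets (40 K/µL), which apply "unless cytopenias are related to bone marrow involvement". Items 2b and 2c allow bilirubin up to 1.5 times the upper limit of normal, "with the exception of Gilbert's Disease and Autoimmune Hemolytic Anemia", and ALT/AST up to 2.5 times, or 5 times with known liver involvement. There is no hemoglobin floor. Subjects from Arms B, C and D enter with progression confirmed by the IRC "after at least two cycles of treatment in trial UTX-TGR-304". Arm A subjects enter without progression.

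Section 10.4 does apply a baseline rule to adverse events: one present before dosing is treatment-emergent only if it worsens or is later judged related. Under 10.5.2 a laboratory value becomes an adverse event only if it is linked to overdose or hospitalization, or if the investigator considers it clinically significant.

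**The concern.** The safety of the combination is an objective (Section 2.1), and Section 10.1 ties safety evaluation to clinically significant changes in laboratory results, among other things. The graded incidence table is the planned subject-level laboratory display that does not depend on investigator judgement, and it does not measure change. A subject who enters with a low platelet count and stays there is counted in the same cell as one who enters normal and falls to that level on treatment.

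Entry abnormality is foreseen by the eligibility criteria, so this is not a rare case. It is also likely to differ by former arm: Arms B, C and D enter with progressive CLL, while Arm A enters non-progressing and already on the combination. A reader comparing columns could take a difference in entry status for a difference in what happened on treatment.

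**Working it through.** The plan states no figure on this point, so there is nothing to reproduce. The check is on the counting rule, followed by an illustration.

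**Do the entry criteria admit out-of-range values?** CTCAE cut-offs are not reproduced in the documents, so I assign no entry grade. The protocol's own thresholds for complete response (Section 8.4, "Peripheral blood counts meeting all of the following criteria") serve as a yardstick: neutrophils above 1.5 and platelets at least 100 × 10⁹/L. The entry floors are 0.75/1.5 = 50% and 40/100 = 40% of these, and no floor applies to marrow-related cytopenia. The liver limits are explicitly above the upper limit of normal. So the answer is yes. (The neutrophil units in item 2a must be reconciled: 750 × 10³/mm³ is 750 K/µL, 1,000 times the bracketed figure. I use the bracketed figure only to describe the text.)

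**Would an entry abnormality be picked up after baseline?** Table 1 schedules 4 + 5 + 2 = 11 hematology draws through cycle 12 (cycle 1, cycles 2–6, cycles 9 and 12). The Cycle 1 Day 1 sample precedes infusion, which leaves 10. Treating draws as independent, a simplification, an abnormality seen at only 20% of draws is counted with probability 1 − 0.8¹⁰ = 0.89 (0.91 with 11 draws). At 50% of draws the probability is 1 − 0.5¹⁰ = 0.999. Capture close to 1 is plausible for a persistent abnormality.

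**How far apart are the two counts?** All four inputs are assumptions:

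- f: share abnormal at entry
- s: share of those abnormal again after baseline
- w: share of those who worsen
- q: new-onset rate among subjects normal at entry

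With all subjects as the denominator throughout:

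- Planned table = f·s + (1 − f)·q
- New or worsened = f·w + (1 − f)·q
- Excess = f·(s − w), which does not depend on q

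With f = 30%, s = 100%, q = 20%:

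- Planned table = 0.30 + 0.70 × 0.20 = 44%
- New or worsened = 0.70 × 0.20 + 0.30w = 14% + 0.30w, which is 14% at w = 0 and 17% at w = 10%

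Over f = 5–40%, s = 70–100% and w = 0–10%, the excess runs from 0.05 × (0.70 − 0.10) = 3 points to 0.40 × (1 − 0) = 40 points.

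**What does this do between arms?** Take the same q = 20% and s = 100% in two groups, one with f = 5% and one with f = 30%. The planned table shows 0.05 + 0.95 × 0.20 = 24% against 44%, a gap of 20 points with the same new-onset rate. At w = 0 the new-or-worsened count shows 0.95 × 0.20 = 19% against 14%. That removes most of the gap but not all of it, because subjects already abnormal have less room to be counted. A shift table, which conditions on baseline grade, shows this directly.

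**The case against.** The case on the other side has substance, and several stronger readings fail.

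- A reader might infer that the laboratory plan ignores baseline altogether. It does not: change from baseline by visit is in the same paragraph. That summary describes groups, however, and cannot show which subjects were already abnormal or who worsened.
- A reader might infer that the plan reports disease at entry as drug toxicity. It does not: the table is of abnormal results and attributes nothing. Attribution runs through adverse events, where Sections 10.3, 10.4, 10.5 and 10.9.5 deal with pre-existing conditions and causality. That route reaches laboratory values only once they are recorded as adverse events.
- A reader might infer that improving subjects are counted at their entry grade. They are counted at their worst post-baseline grade, and not at all if every post-baseline value is in range.
- A reader might set the 44% against the 20% new-onset rate. The denominators differ: 20% applies to subjects normal at entry, and over all subjects it is 14% plus any who worsen.
- A reader might think that rebasing everyone to 204 entry is free of harm. For Arm A that baseline is an on-treatment value (Section 6.1 has them continue from where Study 304 stopped), so abnormalities acquired on the combination would disappear from the count.

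It is also fair that the study is descriptive, with no hypothesis test, and that no decision rule uses this table. That limits how serious the point is. It does not make the table interpretable as it stands.

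**Conclusion.** The point holds for the graded laboratory incidence table. Its counting rule does not condition on baseline, the eligibility criteria admit abnormal values, and no other planned display separates entry abnormalities from new or worsened ones subject by subject. Differences by former arm in that table will partly reflect entry status.

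The size cannot be known from the documents, because the share entering abnormal is not given. Under the assumptions above, the table overstates new or worsened abnormality by 3 to 40 percentage points. In the worked case the excess is 30 points if no entry-abnormal subject worsens and 27 points if 10% do. The excess is zero only if no one enters abnormal, or if everyone who does and is counted also worsens. This is a presentation defect worth correcting in a descriptive study; it does not invalidate the safety analysis as a whole.

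**What to change.** In Section 10.5.2:

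1. Keep the planned table, labelled as post-baseline abnormality regardless of baseline.
2. Add a shift table of baseline grade to worst post-baseline CTCAE grade, by former arm.
3. Add incidence by maximum grade for subjects whose post-baseline grade is new or worse than their baseline grade.
4. Define baseline. For Arms B, C and D, use the last value before the first 204 dose. For Arm A, present the shift both from the Study 304 pre-treatment baseline and from 204 entry.

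The cost is wording and a few extra tables. Screening hematology and chemistry are already required within 14 days of Cycle 1 Day 1, so no visit or sample is added. Arm A needs Study 304 pre-treatment laboratory data to be linked; I assume these exist and are available to the sponsor. The change does not remove other confounding between former arms: prior exposure and disease status still differ, and Arms C and D have already received one component of the combination.

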### 10.5.3 HANDLING OF ADVERSE EVENTS

---

All adverse events resulting in discontinuation from the study should be followed until resolution or stabilization. Subjects should be followed for AEs for 30 calendar days after discontinuation or completion of protocol-specific treatment (either ublituximab and/or umbralisib). All new AEs occurring during this period must be reported and followed until resolution unless, in the opinion of the investigator, these values are not likely to improve because of the underlying disease. In this case, the investigators must record his or her reasoning for this decision in the subject's medical record and as a comment on the eCRF. After 30 days, only AEs, SAEs, or deaths assessed by the investigator as treatment related are to be reported.

## 10.6 SERIOUS ADVERSE EVENTS

---

### 10.6.1 DEFINITIONS OF SERIOUS ADVERSE EVENTS

---

The definitions of serious adverse events (SAEs) are given below. The investigator is responsible for ensuring that all staff involved in the study are familiar with the content of this section.

An SAE or reaction is defined as any untoward medical occurrence that:

- results in death, is immediately life-threatening,
- in-patient hospitalization or prolongation of existing hospitalization,
- results in persistent or significant disability/incapacity, and/or
- causes a congenital anomaly/birth defect.

Medical and scientific judgment should be exercised in deciding whether expedited reporting is appropriate in other situations, such as important medical events that may not be immediately life-threatening or result in death or hospitalization but may jeopardize the subject or may require intervention to prevent one of the other outcomes listed in the previous definition. These should also usually be considered serious. Examples of such events are intensive treatment in an emergency room or at home for allergic bronchospasm; blood dyscrasias or convulsions that do not result in hospitalization; or development of drug dependency or drug abuse.

Progression of malignancy (including fatal outcomes), if documented by use of appropriate method (for example, as per IWCLL [Hallek et al. 2008](#), should not be reported as a serious adverse event.

A suspected unexpected serious adverse reaction (SUSAR) is defined as an SAE that is suspected to be at least possibly related to study medication(s) and is an unexpected event. SUSAR reporting is encompassed within SAE reporting guidelines as defined in this section.

Treatment within or admission to the following facilities is not considered to meet the criteria of “in-patient hospitalization” (although if any other SAE criteria are met, the event must still be treated as an SAE and immediately reported):

- Emergency Department or Emergency Room
- Outpatient or same-day surgery units
- Observation or short-stay unit
- Rehabilitation facility
- Hospice or skilled nursing facility
- Nursing homes, Custodial care or Respite care facility
- Admissions to receive protocol defined therapy

Hospitalization during the study for a pre-planned surgical or medical procedure (one which was planned prior to entry in the study), does not require reporting as a serious adverse event to the Sponsor.

---

## 10.6.2 SERIOUS ADVERSE EVENT REPORTING BY INVESTIGATORS

---

It is important to distinguish between “serious” and “severe” adverse events, as the terms are not synonymous. Severity is a measure of intensity; however, an AE of severe intensity need not necessarily be considered serious. For example, nausea which persists for several hours may be considered severe nausea but may not be considered an SAE. On the other hand, a stroke which results in only a limited degree of disability may be considered only a mild stroke but would be considered an SAE. Severity and seriousness should be independently assessed when recording AEs and SAEs on the eCRF.

Adverse events classified by the treating investigator as **serious** require expeditious handling and reporting to the Sponsor in order to comply with regulatory requirements. Serious adverse events may occur at any time from the signing of the informed consent form through the 30-day follow-up period after the last study treatment. Sponsor or designee should be notified of all SAEs, regardless of causality, within 24 hours of the first knowledge of the event by the treating physician or research personnel.

### **To report an SAE, see the appropriate form.**

All SAEs (regardless of causality assessment) occurring on study or within 30 days of last study treatment should be immediately reported to the sponsor as SAEs within the CRF and followed until resolution (with autopsy report if applicable).

CLL progression or death due to CLL progression should be reported by the investigator as a serious adverse event only if it is assessed that the study drugs caused or contributed to the CLL progression (i.e. by a means other than lack of effect). Unrelated events of CLL progression should be captured on the appropriate eCRF.

The investigator must review and sign off on the SAE data on the SAE report. The SAE should be reported to the Sponsor (or Sponsor designee) as outlined in the Safety Monitoring Plan.

When an SAE is reported to the sponsor or designee, the same information should be entered on the eCRF within 24 hours (1 business day). Transmission of the SAE report should be confirmed by the site personnel submitting the report.

Follow-up information for SAEs and information on non-serious AEs that become serious should also be reported to the sponsor or designee as soon as it is available; these reports should be submitted using the appropriate SAE form. The detailed SAE reporting process will be provided to the sites in the Safety Monitoring Plan.

Investigators must report SAEs and follow-up information to their responsible Institutional Review Board (IRBs)/Independent Ethics Committee according to the policies of the responsible IRB (Research Ethics Committee).

---

## 10.7 SPONSOR SAE REPORTING REQUIREMENTS

---

Sponsor is responsible for reporting relevant SAEs to the competent authority, other applicable regulatory authorities, and participating investigators, in accordance with ICH guidelines, FDA regulations, and/or local regulatory requirements.

Sponsor is responsible for reporting unexpected fatal or life-threatening events associated with the use of the study drugs to the regulatory agencies and competent authorities within 7 calendar days after being notified of the event. The Sponsor will report all related but unexpected SAEs including non-death/non-life-threatening related but unexpected SAEs (SUSAR) associated with the use of the study medications to the regulatory agencies and competent authorities by a written safety report within 15 calendar days of notification. Following the submission to the regulatory agencies and competent authorities, Investigators and trial sites will be notified of the SUSAR. Investigators must report SUSARs and follow-up information to their responsible Institutional Review Board (IRBs)/Independent Ethics Committee according to the policies of the responsible IRB (Research Ethics Committee).

## 10.8 RECORDING OF ADVERSE EVENTS AND SERIOUS ADVERSE EVENTS

---

Investigators should use correct medical terminology/concepts when recording AEs or SAEs on the SAE Report Forms and AE eCRF. Avoid colloquialisms and abbreviations.

All AEs, including those that meet SAE reporting criteria, should be recorded on the AE eCRF; AEs that meet the definition of an SAE should additionally be reported.

## 10.9 DIAGNOSIS VS. SIGNS AND SYMPTOMS

---

All AEs should be recorded individually in the subject's own words (verbatim) unless, in the opinion of the Principal Investigator or designated physician, the AEs constitute components of a recognized condition, disease, or syndrome. In the latter case, the condition, disease, or syndrome should be named rather than each individual sign or symptom. If a constellation of signs and/or symptoms cannot be medically characterized as a single diagnosis or syndrome at the time of reporting, each individual event should be recorded as an AE or SAE as appropriate on the relevant form(s) (SAE Report Form and/or AE eCRF). If a diagnosis is subsequently established, it should be reported as follow-up information is available. If a diagnosis is determined subsequent to the reporting of the constellation of symptoms, the signs/symptoms should be updated to reflect the diagnosis.

---

